Prospective, Randomized, Multi-Center Trial of
Higher End-expiratory Lung Volume/Lower FiO₂
versus Lower End-expiratory Lung Volume/ Higher
FiO₂ Ventilation in Acute Lung Injury and Acute
Respiratory Distress Syndrome

*Assessment of Low tidal Volume and elevated
End-expiratory volume to Obviate Lung Injury
(ALVEOLI)*

ARDS Clinical Network
ARDSNet Study 04, Version I
Copyright 1999 ARDS Clinical Network
ACTIVE RESEARCH PROTOCOL

July 20, 1999

Please note the correction to the following typographical error in the protocol:

Page 34, Section 6: Statistical Considerations

Second paragraph, third sentence currently reads: The trial may be stopped by the DSMB for futility of the Higher ELV/Lower FiO₂ strategy at the first interim analysis if mortality in the Higher ELV/Lower FiO₂ group is **less** than that observed in the Lower ELV/Higher FiO₂ group.

The CORRECT wording should read: The trial may be stopped by the DSMB for futility of the Higher ELV/Lower FiO₂ strategy at the first interim analysis if mortality in the Higher ELV/Lower FiO₂ group is **MORE** than that observed in the Lower ELV/Higher FiO₂ group.

3.6	Randomization	18
3.7	Minorities/Women	18
4	Study Procedures	19
4.1	Ventilator Procedures	19
4.1.1	Volume Cycled Ventilation	19
4.1.2	Weaning	24
4.1.3	Completion of ventilator procedures.	28
4.1.4	Premature withdrawal from treatment	29
5	Data Collection	29
5.1	Background Assessments	29
5.2	Baseline Assessments	29
5.3	Assessments During Enrollment	31
5.3.1	Ventilator Protocol Monitoring	33
5.4	Endpoint Determinations	34
6	Statistical Considerations	34
7	Data Collection and Site Monitoring	35
7.1	Data collection	35
7.2	Reporting of adverse events	36
7.3	Site monitoring	36
8	Risk Assessment	37

9 Human Subjects	37
10 Appendices	42
A Exclusion criteria definitions	42
B Adverse Event Reporting Procedure	44
C Schedule of Events	46
D Procedures for PEEP and FiO₂ adjustments when PEEP/FiO₂ is not compatible with protocol.	47
E Genetic Testing Information	48

Part I

Study Summary

- **Title:** Prospective, Randomized, Multi-Center Trial of Higher End-expiratory Lung Volume/Lower FiO₂ versus Lower End-expiratory Lung Volume/Higher FiO₂ Ventilation in Acute Lung Injury and Acute Respiratory Distress Syndrome.
- **Objectives:** To compare clinical outcomes of patients with acute lung injury and acute respiratory distress syndrome treated with a higher end-expiratory lung volume/lower FiO₂ versus a lower end-expiratory lung volume/higher FiO₂ ventilation strategy.
- **Hypothesis (Ho):** Mortality from ALI/ARDS will be the same in patients treated with a higher end-expiratory lung volume/lower FiO₂ ventilation strategy as in patients treated with a lower end-expiratory lung volume/higher FiO₂ ventilation strategy.
- **Study Design:** Multi-Center, prospective, randomized, controlled clinical trial.
 1. Enrollment: approximately 24 months.
 2. Patients will be treated for 28 days or until they achieve unassisted breathing.
 3. Patients will be followed for 60 days or until discharged home with unassisted breathing.
- **Sample Size/Interim Monitoring:**
 1. The study will accrue a maximum of 750 patients.
 2. Progress of the trial will be reviewed by an independent Data and Safety Monitoring Board to determine if randomization should stop for futility, lack of safety, or proven efficacy. Interim analyses will be conducted after completion of the study procedures in approximately 250 and 500 patients. Stopping for futility or efficacy will be based on formal group sequential stopping boundaries.
- **Inclusion Criteria:** Acute Onset of:

1. $\text{PaO}_2/\text{FiO}_2 \leq 300$ (adjusted for barometric pressure).
2. Bilateral infiltrates consistent with pulmonary edema on frontal chest radiograph.
3. Requirement for positive pressure ventilation through an endotracheal tube.
4. No clinical evidence of left atrial hypertension. If measured, pulmonary arterial wedge pressure ≤ 18 mmHg.

● **Exclusion Criteria:**

1. Clinicians caring for patient refuse to use Volume Assist/Control ventilation for at least 12 hours.
2. Age < 13 years.
3. Participation in other intervention trials in ALI, ARDS, or sepsis within the previous 30 days.
4. > 36 hours since all inclusion criteria are met.
5. Neuromuscular disease that impairs ability to ventilate without assistance, such as C5 or higher spinal cord injury, amyotrophic lateral sclerosis, Guillain-Barre syndrome, and myasthenia gravis.
6. Pregnancy (negative pregnancy test required for women of child-bearing potential).
7. Increased intracranial pressure, tricyclic antidepressant overdose (if most recent blood level elevated or no blood level available), Hgb SS, Hgb SC, or other conditions where hypercapnia would be contraindicated.
8. Severe chronic respiratory disease.
9. Morbid obesity.
10. Burns $\geq 30\%$ total body surface area.
11. Malignancy or other irreversible disease or condition for which 6-month mortality is estimated $\geq 50\%$.
12. Bone marrow transplant.
13. Lung transplant.
14. Not committed to full support.
15. Severe chronic liver disease (Child-Pugh Score of 10 -15).
16. Vasculitis with diffuse alveolar hemorrhage.

- **Efficacy:** The primary efficacy variable is mortality prior to hospital discharge to 60 days.

Secondary efficacy variables include:

1. Ventilator Free Days, which is the number of days of unassisted breathing after initiating spontaneous breathing to day 28 after randomization (if at least 48 consecutive hours unassisted breathing were achieved). This efficacy measure is related to differences in mortality, morbidity, and cost attributable to differences in time to recovery from respiratory failure or time to death.
2. Percentage of patients who achieve 48 consecutive hours unassisted breathing prior to 28 days.
3. Number of ICU-free days from randomization to day 28.
4. Number of Organ Failure Free Days from randomization to day 28 (renal, hepatic, central nervous system, coagulation, circulation).
5. Number of days meeting commence-weaning criteria from randomization to day 28.
6. Number of days after initially achieving unassisted breathing from randomization to day 28.
7. Incidence of barotrauma (pneumothoraces, pneumatoceles > 2 cm largest diameter, pneumomediastinum).
8. Percentage of patients discharged alive from hospital.
9. Mortality and days of unassisted breathing for patients with pre- randomization $\text{PaO}_2/\text{FiO}_2 \leq 200$.

Part II

Study Description

Large Prospective, Randomized, Multi-Center Trial of Higher End-expiratory Lung Volume/Lower FiO₂ versus Lower End-expiratory Lung Volume/Higher FiO₂ Ventilation in Acute Lung Injury and Acute Respiratory Distress Syndrome

Protocol for the NIH NHLBI ARDS Network July 20, 1999

1 Background

Acute lung injury (ALI) and acute respiratory distress syndrome (ARDS) occur when an event such as sepsis or massive aspiration causes inflammation, increased pulmonary vascular permeability, and extravasation of protein-rich fluid into the pulmonary interstitium and alveolar space [1]. The inflammatory process causes inactivation, destruction, and decreased production of surfactant [2],[3]. This leads to increased surface tension at the alveolar air-fluid interface, which causes microatelectasis. Chest radiographs in ALI and ARDS patients are frequently interpreted to demonstrate diffuse disease. However, CT images, histologic sections, and physiologic studies indicate that the disease is patchy [4],[5]. Much of the ALI/ARDS lung is atelectatic or filled with extravascular fluid and is unavailable for ventilation and gas exchange. Other lung regions appear to be normal. Arterio-venous shunt, ventilation-perfusion imbalance, and high dead-space cause severe abnormalities of gas exchange. Management of acute respiratory failure frequently requires positive pressure ventilation to ensure adequate gas exchange. Despite aggressive treatments for the conditions that precipitate ALI/ARDS, many patients die without resolution of the lung injury.

1.1 Use of PEEP and FiO₂ to Support Arterial Oxygenation.

Patients with ALI/ARDS usually receive positive end-expiratory pressure (PEEP) and increased fractions of inspired oxygen (FiO₂) to support arterial oxygenation during mechanical ventilation for acute respiratory failure. However, there are adverse effects of both PEEP and increased FiO₂. Oxygen toxicity from high FiO₂ may cause or worsen acute lung injury [6]-[8]. PEEP allows use of lower FiO₂ and may decrease the risk of oxygen toxicity. However, PEEP may cause circulatory depression from both decreased venous return and increased right ventricular afterload [9]. Moreover, because peak airway pressures and lung volumes increase with increases in PEEP, higher PEEP may increase the risks of barotrauma and stretch-induced lung injury [10]. These risks of PEEP can be modulated by limiting peak inspiratory airway pressures and volumes. However, with both higher PEEP and limited peak airway pressures and volumes, tidal volumes may be very small, leading to severe hypercapnia and acidosis.

1.2 Ventilation-Associated Lung Injury (VALI).

Several studies in animals and humans demonstrated that acute lung injury may be exacerbated or perpetuated by mechanical ventilation [11]-[16]. However, modifications to traditional strategies of mechanical ventilation may attenuate or prevent VALI [11],[16]-[18].

1.2.1 VALI from excessive lung stretch.

When traditional tidal volumes of 10-15 ml/kg are administered to ALI/ARDS patients, the patent air-spaces are distended much more than during normal ventilation. The high airway pressures typically observed in ALI/ARDS patients reflect distention of intrapulmonary air-spaces.

stretching of normal lung tissue causes parenchymal inflammation [13], increased vascular permeability [19], accumulation of lung water [20], alveolar flooding and atelectasis [11],[13], radiographic infiltrates [14], and hypoxemia from right-to-left shunting of blood [14]. These findings are very similar to those observed in ALI and ARDS patients. This suggests

that stretch-induced lung injury may exacerbate or prevent resolution of ALI and ARDS. Many clinicians and investigators have recommended avoiding high peak airway pressures and volumes to reduce stretch-induced lung injury [21]-[23] . This can be achieved by using smaller tidal volumes or lower levels of PEEP. Three recent trials of reduced tidal volume ventilation did not demonstrate improved clinical outcomes [24]-[26] . However, a recently completed larger, multicenter, randomized trial by the NIH NHLBI ARDS Network demonstrated a 20% reduction in mortality with a reduced tidal volume ventilation strategy. This strategy will be used in both arms of the proposed study.

1.2.2 VALI from ventilation with low end-expiratory lung volumes.

Several studies in animals suggest that VALI may occur from injurious mechanical forces in small bronchioles and alveoli that repeatedly snap open and close with each tidal breath or from cyclic application of high stress in the parenchyma at the margins between diseased and normal lung regions [11],[17],[18]. In several animal models of acute lung injury, VALI was attenuated or prevented when PEEP was used during mechanical ventilation. PEEP may protect the lung from VALI by recruiting and maintaining patency of small atelectatic or fluid-filled bronchioles and alveoli [16]-[18], preventing the injurious mechanical forces that occur when these airways repeatedly open during inspiration and collapse during expiration.

It is unclear what level of PEEP is necessary to achieve optimal lung protective effects. Some investigators have recommended construction of static or quasi-static inspiratory pressure-volume curves in ALI/ARDS patients to understand the pressures and volumes at which small bronchioles and alveoli open (Figure 1).

The slope of this curve, dV/dP , is the compliance of the respiratory system (lungs and chest wall). The increasing-slope of the lower portion of the curve represents recruitment (opening) of previously atelectatic or fluid-filled airways. The term “Pflex” is frequently used to indicate the pressure at the mid-point of this portion of the curve. Some investigators have recommended that PEEP should be raised to $P_{flex} + 2 \text{ cmH}_2\text{O}$ in ALI and ARDS patients to achieve and maintain high levels of lung

Figure 1: Respiratory System Pressure-Volume Curve

recruitment, to prevent VALI from ventilation with repeated airway collapse at end-expiration [27]. This recommendation is problematic for several reasons: 1) In many patients, there is no increasing-slope portion of the pressure-volume curve; hence, no P_{flex} can be identified [28]. 2) In many patients, the increasing-slope portion of the curve reflects properties of the chest wall, not the lung [29]. 3) The pressure-volume relationship during tidal ventilation is different from the static or quasi-static inspiratory pressure-volume relationship [28]. 4) Recruitment of small airways continues as airway pressure and volume rise well above P_{flex} + 2 cmH₂O [30]. Higher PEEPs may achieve higher recruitment, but only at the risk of PEEP-induced circulatory depression, increased risk of barotrauma and stretch-induced lung injury, and decreased alveolar ventilation. 5) Refined pressure-volume assessments may eventually identify volumes and pressures with high lung recruitment, but this approach will provide no insight regarding potential adverse effects of PEEP or how to balance the salutary lung protective effects with the adverse effects of PEEP.

The pressure-volume characteristics of the lungs demonstrate hysteresis (at any airway pressure, volume is greater during deflation than during inflation). This is attributed to the differences in opening and closing

pressures of small bronchioles and alveoli: opening pressures are higher than closing pressures [31]-[33]. This behavior is exaggerated in acute lung injury [31]. Thus, many airways in patients with ALI/ARDS may close and remain closed until opened with a relatively high transpulmonary pressure (recruitment maneuver, RM). These airways may then remain open for some time during ventilation at lower transpulmonary pressures. Some workers have recently recommended using RMs in ARDS patients to promote ventilation at higher end-expiratory volumes, to reduce the risk of VALI from ventilating with atelectasis at end-expiration.

A study by Amato et al. [34] showed improved survival in a group of ARDS patients treated with a lung protective strategy that used higher PEEP (Pflex + 2 cmH₂O), recruitment maneuvers, and limited peak inspiratory stretch (tidal volume < 6 ml/kg; peak inspiratory pressure < 40 cmH₂O). In the control group strategy, PEEP was used in a traditional manner to support arterial oxygenation; no recruitment maneuvers were conducted; tidal volumes were 12 ml/kg. This study was small (53 patients), and mortality in the control group (71%) was higher than in recent trials of ALI/ARDS when lung protective ventilation strategies were not used [24]-[26]. Therefore, it is unclear if the lower mortality with the lung protective strategy was due to the method of PEEP adjustment, recruitment maneuvers, limitation of peak inspiratory stretch, or randomization of more high-risk patients to the traditional ventilation strategy.

1.3 Summary: balancing benefits and risks of different strategies

Because of the increasing evidence for lung injury from ventilation with repeated collapse of bronchioles and alveoli at end-expiration, some clinicians and investigators now recommend an approach to mechanical ventilation in which end-expiratory lung volume is maintained at higher levels than have been traditionally targeted. This may be achieved with higher PEEPs than have been commonly used to support arterial oxygenation; and by introducing periodic recruitment maneuvers. With this approach, lower FiO₂s are necessary to support arterial oxygenation but there may be adverse effects on circulation, acid-base balance, and lung stretch. Other clinicians and investigators favor a more traditional

approach that utilizes lower PEEPs and higher FiO_2 s. The two approaches represent different prioritization schemes for several clinical objectives that must be considered in the care of all ALI/ARDS patients:

Higher End-expiratory Lung Volume/Lower FiO_2 (Higher ELV/Lower FiO_2) Prioritization Scheme

- High priority to prevention of VALI from ventilation with repeated airway collapse at end-expiration.
- High priority to prevention of lung injury from oxygen toxicity.
- Lower priority to prevention of VALI from inspiratory stretch.
- Lower priority to maintaining normal arterial PCO_2 and pH.
- Lower priority to prevention of PEEP-induced circulatory depression.

Lower End-expiratory Lung Volume/Higher FiO_2 (Lower ELV/Higher FiO_2) Prioritization Scheme

- High priority to prevention of VALI from inspiratory stretch.
- High priority to maintenance of normal arterial PCO_2 and pH.
- High priority to prevention of PEEP-induced circulatory depression.
- Lower priority to prevention of VALI from ventilation with repeated airway collapse at end-expiration.
- Lower priority to prevention of lung injury from oxygen toxicity.

There is little information from clinical studies to guide clinicians who must balance the risks and benefits of the two approaches to mechanical ventilation. The proposed study will provide useful information to clinicians by comparing important clinical outcomes in ALI/ARDS patients treated with the two different approaches.

Hypothesis (Ho) Mortality from ALI/ARDS will be equivalent with the two ventilation strategies.

2 End-Points

The primary efficacy measure is mortality prior to hospital discharge to day 60 after randomization. Patients alive in hospital at day 60 will be considered to have survived. This efficacy measure has been used to calculate sample size and to develop interim stopping boundaries.

Since survival ALI/ARDS patients may be affected by many other factors that are indirectly or remotely related to mortality, several secondary outcome variables will also be examined. These are chosen to reflect morbidity and cost of medical care:

1) Number of Ventilator Free Days (VFDs): the number of days after initiating unassisted breathing to day 28 after randomization, assuming a patient survives for at least 48 consecutive hours after initiating unassisted breathing. For example, if a patient initiates unassisted breathing on day 16 and survives to day 28, he/she will be assigned a value of 12 VFDs. If a similar patient begins unassisted breathing on day 16 but dies on day 25, he/she will be assigned a value of 9 VFDs. If a patient survives for > 48 consecutive hours of unassisted breathing but requires assisted breathing (for any reason) before day 28, he/she will be assigned only the number of days of unassisted breathing before day 28. Patients who die without initiating unassisted breathing or before 48 consecutive hours of unassisted breathing will be assigned a value of zero VFDs. Patients transferred to another hospital or other health care facility prior to day 28 (intermediate care, nursing home etc.) while still on positive pressure ventilation will be followed to assess this efficacy measure.

VFDs is related to the “days of assisted ventilation”, which would be a simpler measure. However, if there were a trend in one treatment group towards more rapid death on assisted ventilation, the effect of this trend on days of assisted ventilation would be misleading. “Average duration of ventilation in survivors” would avoid this potential problem. However, if there were a trend towards lower mortality in one treatment group with greater days of assisted ventilation in survivors in that group, the measure of days of assisted ventilation in survivors would be misleading. VFDs will be favorably affected by both lower mortality and shorter duration of ventilation in survivors.

- 2 Percentage of patients who achieve 48 consecutive hours of unassisted breathing at 28 days after randomization
- 3 Number of ICU-free days at 28 days after randomization.
- 4 Number of Organ Failure Free days at 28 days after randomization, using previously validated definitions for renal, central nervous, coagulation, circulation, and hepatic organ and system failures [35], [36].
- 5 Number of days between the day of first meeting criteria to commence-weaning and day 28 after randomization.
- 6 Number of days between the day of initially achieving unassisted ventilation and day 28 after enrollment.
- 7 Incidence of barotrauma (pneumothoraces, pneumatoceles > 2 cm largest diameter, pneumomediastinum).
- 8 Percentage of patients discharged alive from hospital. Patients alive in hospital at 60 days will be considered to have been discharged alive.
- 9 Mortality and days of unassisted breathing with pre-randomization $\text{PaO}_2/\text{FiO}_2 \leq 200$.

3 Study Population and Enrollment

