If criteria 1-5 are met for > 120 minutes, unassisted breathing will continue (step 4.1.2.6). If any of criteria 1-5 are not met during the 120 minute trial, then PS will resume at 5 cmH₂O and tolerance will be reassessed (step 4.1.2.3).

4.1.2.6 Definition of unassisted breathing.

1. Extubated with face mask, nasal prong oxygen, or room air, OR
2. T-tube breathing, OR
3. Tracheostomy mask breathing, OR
4. CPAP = 5 without PS or IMV assistance.

4.1.3 Completion of ventilator procedures.

Patients will be considered to have completed the study ventilator procedures if any of the following conditions occur:

1. Death.
2. Hospital discharge.
3. Alive 28 days after randomization.

If a patient requires positive pressure ventilation after a period of unassisted breathing, the study ventilator procedures for the group to which the patient was randomized will resume unless the patient was discharged from the hospital or > 28 days elapsed since enrollment.

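### The lead sentence of the Section 2 ventilator-free-day definition tests 48 hours of survival, not 48 hours of unassisted breathing, and it alone reaches survivors who fail early

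*Supplement*

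**What the plan says.** The protocol defines VFDs, its first secondary outcome, in two places.

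- **Study Summary, Efficacy, secondary variable 1.** The count is "the number of days of unassisted breathing after initiating spontaneous breathing to day 28 after randomization", and the condition is "if at least 48 consecutive hours unassisted breathing were achieved".
- **Section 2, item 1, lead sentence.** The count is "the number of days after initiating unassisted breathing to day 28 after randomization", and the condition is "assuming a patient survives for at least 48 consecutive hours after initiating unassisted breathing".

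Item 1 then adds three things.

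- Worked examples. The first reads: "if a patient initiates unassisted breathing on day 16 and survives to day 28, he/she will be assigned a value of 12 VFDs". The second has the same start, death on day 25, and 9 VFDs.
- A relapse rule, which opens "If a patient survives for > 48 consecutive hours of unassisted breathing but requires assisted breathing (for any reason) before day 28" and credits only the unassisted days before day 28.
- A zero rule: "Patients who die without initiating unassisted breathing or before 48 consecutive hours of unassisted breathing will be assigned a value of zero VFDs".

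Secondary outcome 2 is the percentage of patients who reach 48 consecutive hours of unassisted breathing. Section 5.4 records when unassisted breathing began and a status 48 hours later. It does not say whether status means alive or still unassisted. None of the amendments changes the VFD definition.

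**The concern.** The Summary's condition concerns breathing, while the Section 2 lead sentence asks only whether the patient is alive. The two part for patients who come off assistance, go back on within 48 hours and survive. The protocol foresees return to ventilation: Section 4.1.3 resumes the study ventilator procedures when a patient needs positive pressure again after breathing unassisted.

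Taken at its word, the lead sentence credits ventilated days as ventilator-free, and an early failure can outrank a later one. That defeats the purpose given in Section 2, which is that VFDs should respond to lower mortality and to shorter ventilation in survivors. The same patient would also count as a failure on secondary outcome 2 while scoring highly on outcome 1. Two analysts following different sentences could produce different VFD results from the same data.

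**Working it through.** **Inputs.** The rules are those of the Study Summary and Section 2, item 1. The patients below are hypothetical, apart from the plan's own two examples.

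**Step 1: reproduce the plan's figures.**
- Start day 16, alive at day 28: 28 − 16 = 12.
- Start day 16, death on day 25: 25 − 16 = 9.

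Both match. With breathing sustained throughout, both definitions give these scores, so the examples do not settle the disputed case.

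**Step 2: find the Section 2 sentence that reaches a survivor re-ventilated within 48 hours.**
- Relapse rule: does not apply, because it needs more than 48 hours of unassisted breathing.
- Zero rule: does not apply, because it is limited to patients who die.
- Lead sentence: applies, because the patient was alive 48 hours after starting.

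**Step 3: score patients who start on day 10 and are alive at day 28.**

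| Course | Section 2, literal | Summary |
|---|---|---|
| Never re-ventilated | 28 − 10 = 18 (lead sentence) | 18 |
| Re-ventilated at 72 h (day 13), ventilated through day 28 | 13 − 10 = 3 (relapse rule) | 3 |
| Re-ventilated at 24 h (day 11), ventilated through day 28 | 28 − 10 = 18 (lead sentence) | 0 (inferred) |

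The third patient had 11 − 10 = 1 day off assistance and 28 − 11 = 17 days on it. The literal score equals that of the patient who never went back. It exceeds the 3 given to the patient who lasted longer, and the 12 of the plan's own day-16 success. The Summary's zero is inferred: the condition is not met, but the Summary does not state a value.

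**Step 4: the same kind of failure, followed by success.** The patient starts on day 16, is re-ventilated on day 17, and is unassisted again from day 20 to day 28.
- Lead sentence: 28 − 16 = 12.
- Summary, counting from the qualifying period: 28 − 20 = 8.
- Summary, counting all unassisted days: 8 + (17 − 16) = 9.

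Here both definitions give a positive score and differ by 3 or 4 days. The 8-or-9 choice shows that the Summary also leaves the starting point of the count open.

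**The case against.** The strongest reply is that the item, read as a whole, points one way. The relapse rule speaks of surviving for more than 48 hours of unassisted breathing, which suggests that survival in the lead sentence was loose shorthand for staying off assistance. The zero rule, the Summary and secondary outcome 2 all use hours of breathing. Crediting 17 ventilated days as ventilator-free is implausible, and it would make VFDs nearly duplicate outcome 6, which already counts from first unassisted breathing to day 28.

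Much of this stands. A careful analyst would probably adopt the Summary's rule. Section 2 is inconsistent within itself and has no express rule for this case, rather than being a rival definition throughout. But the intended rule has to be inferred against the only sentence that reaches the patient. No separate analysis plan is shown, and scoring detail is often left to one; here, however, the protocol states a rule that misscores, which is more than missing detail.

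Three stronger readings are tempting, and the documents do not support them.

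- **That every early failure who lives is scored in opposite ways.** Full credit against zero arises only for survivors who never complete 48 hours. The others differ in size, as in Step 4.
- **That a failed spontaneous breathing trial starts the VFD clock.** Section 4.1.2.6 does list "CPAP = 5 without PS or IMV assistance" as unassisted breathing. But Section 4.1.2.5 calls the attempt a trial and leads to 4.1.2.6 only after more than 120 minutes of success. The point is arguable, not established.
- **That mean VFDs move by a known amount.** If 5–20% of patients were affected by 5–10 days each, the mean would shift by 0.05 × 5 = 0.25 to 0.20 × 10 = 2.0 days. Those inputs are assumptions, and the result is a pooled shift, not a difference between arms.

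**Conclusion.** The inconsistency is real and worth correcting. The lead sentence of Section 2, item 1 conflicts with the Summary, with the threshold in its own later sentences and with secondary outcome 2. Taken literally, it misscores survivors who return to assisted breathing within 48 hours. In the day-10 example the score is 18, against 3 for a later failure under the relapse rule and an inferred 0 under the Summary.

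These are scores for individual hypothetical patients under a literal reading. The documents give no early-failure rate in either arm, so neither the effect on mean VFDs nor that on the treatment comparison can be sized, and no effect on a trial conclusion is shown. The point is confined to a secondary outcome. The primary mortality analysis, the sample size and the stopping boundaries do not depend on it.

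**What to change.** Amend Section 2, item 1 as follows.

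1. Replace the survival condition in the lead sentence with completion of at least 48 consecutive hours of unassisted breathing.
2. Count only days of unassisted breathing, from the start of the first period that meets the threshold, up to day 28. This is a design choice as well as a reconciliation, because the Summary does not fix the starting point.
3. Assign zero to any patient, alive or dead, who completes no such period by day 28.
4. Confirm that the 48-hour status in Section 5.4 records whether the patient is still breathing unassisted, and that return-to-ventilation dates are captured. Section 5.4 does not list those dates, although the existing relapse rule already needs them.

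The cost is a short change of wording, with the Summary aligned to match, and a check of the case report form. If return dates are already collected for the relapse rule, no new data are needed; if not, the gap exists under the current text too.
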